4.2.3 Exploratory Endpoints

There are no exploratory endpoints in this study.

5 Study Enrollment and Withdrawal**5.1 Inclusion Criteria**

In order to be eligible to participate in this study (experimental arm), an individual must meet all of the following criteria:

1. Age 0 to 24 months
2. Admitted to the general inpatient pediatrics unit
3. Has a diagnosis of acute bronchiolitis
4. Receiving supplemental oxygen support

Data collected for the control arm will be obtained via retrospective chart review for patients meeting the following inclusion criteria:

1. Age 0 to 24 months
2. Admitted to the general inpatient pediatrics unit

3. Has a diagnosis of acute bronchiolitis
4. Receiving supplemental oxygen support

5.2 Exclusion Criteria

An individual who meets any of the following criteria will be excluded from participation in this study:

1. Admitted to the pediatric intensive care unit
2. Has an underlying pre-existing condition that may affect the respiratory system (includes bronchopulmonary dysplasia, reactive airways disease, asthma, restrictive lung diseases, other chronic lung diseases, etc.)
3. Has other comorbid conditions upon admission that may affect the respiratory system (includes pneumonia or other bacterial or fungal lung infections, acute exacerbation of reactive airways disease, acute exacerbation of asthma, pulmonary edema, pleural effusion, etc.)
4. Has an absolute contraindication to nebulized 3% hypertonic saline, for example, a history of an allergic or anaphylactic reaction
5. Is receiving other respiratory treatments such as bronchodilator treatments (i.e. albuterol or levalbuterol)
6. Is receiving other adjuvant therapy such as antibiotics, antivirals, glucocorticoids, corticosteroids, or diuretics

A potential study subject in the control arm via retrospective chart review who meets any of the following criteria will be excluded from this study:

1. Admitted to the pediatric intensive care unit
2. Has an underlying pre-existing condition that may affect the respiratory system (includes bronchopulmonary dysplasia, reactive airways disease, asthma, restrictive lung diseases, other chronic lung diseases, etc.)
3. Has other comorbid conditions upon admission that may affect the respiratory system (includes pneumonia or other bacterial or fungal lung infections, acute exacerbation of reactive airways disease, acute exacerbation of asthma, pulmonary edema, pleural effusion, etc.)
4. Has an absolute contraindication to nebulized 3% hypertonic saline, for example, a history of an allergic or anaphylactic reaction
5. Is receiving other respiratory treatments such as bronchodilator treatments (i.e. albuterol or levalbuterol)
6. Is receiving other adjuvant therapy such as antibiotics, antivirals, glucocorticoids, corticosteroids, or diuretics

5.3 Vulnerable Subjects

This study involves the pediatric population and will thus include vulnerable subjects.

Under Code of Federal Regulation guidelines, in accordance to 45 CFR 46.405, this study has been determined as a research study that involves greater than minimal risk with potential of direct benefit to individual subjects.

This study utilizes nebulized 3% hypertonic saline treatments and chest percussion therapy, both as previously described in section 2 of this protocol, have very minimal and transient side effects, if any, and are not associated with any serious adverse events.

Because this study involves pediatric participants age 0 to 24 months, assent cannot be assessed or given. Permission and consent from parents or legal guardians will be obtained as set forth in HHS regulations at 45 CFR 46.408.

This proposed research poses a greater than minimal risk with the potential for direct benefit to subjects. 3% hypertonic saline nebulization treatments have been used and studied previously in children with acute bronchiolitis and have not been shown to cause any serious adverse effects and may improve severity of illness. Chest physiotherapy via a chest percussor cup is a non-invasive and gentle technique that has been used and studied previously in children with acute bronchiolitis and have not been shown to cause any serious adverse effects.

5.4 Strategies for Recruitment and Retention

Recruitment strategies include identifying patients upon admission to the general inpatient pediatrics unit with the primary diagnosis of acute bronchiolitis that do not meet exclusion criteria for this study. No media services will be required. If a subject requests information regarding opting out of further recruitment for all research, subjects will be directed to contact [contact] or [name].

Informed consent will be obtained at time of admission within private space of patient room and will be conducted in a sensitive manner, allowing consent to be provided in a clearly explained manner. Ample time will be provided for caregivers to decide on consent.

Information collected will be from the patient's medical chart to include age and gender. No other personal information will be required for this study. Only the primary investigator and any future added co-investigators of this study will receive this information. The target sample size for this experimental arm will be 114 patients and it is anticipated that approximately 200 patients will be screened to achieve this number. The source of participants will only be in the general inpatient pediatrics unit.

Upon patients' enrollment into the study, physicians on the patients' care team will be notified via in person or secure chat through the electronic medical record within 1 hour from patients' enrollment into the study and investigators will obtain clearance from these providers to begin the study treatments.

These physicians will also be notified at this time that they will be asked to answer subjective surveys assessing their patients' response to the study treatment. See Appendix 3.

Parents or caregivers or legal guardians of patients enrolled in this study will be approached at least once by the principal investigator or co-investigators while their child is undergoing study treatments. The timing of this encounter may vary and this encounter is to serve as a means to conduct the subjective caregiver interview. See Appendix 4. Investigators will aim to conduct the subjective caregiver survey at least once while their child is enrolled in the study and ideally will aim to conduct this interview once the child has received the study treatment for at least 24 hours. Parents/caregivers/legal guardians will be approached in a sensitive and calm manner by the principal investigator or co-investigators, and investigators will coordinate this timing with the care team as to not disrupt patient care responsibilities of physicians or nurses.

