4.1 Description of Study Design

Groups:

1. Control group: Patients meeting criteria as above prior to start date, beginning 12 months prior to start date of study, will be examined via retrospective chart review

2. Experimental group: All patients meeting criteria as above beginning start date of study will be enrolled in study to receive adjuvant therapy with 3% hypertonic saline nebulization treatments combined with 3 minutes of chest physiotherapy.

Statistical Methods:

Descriptive statistics (mean \pm standard deviation or median [25th, 75th percentiles] for continuous variables; frequencies and percentages for categorical variables) will be calculated separately by group. The two groups will be compared using the chi-square test or Fisher's exact test, as deemed appropriate, for categorical variables and the two-sample t-test or Mann-Whitney test for continuous data.

For all analyses, the standard assumptions of Gaussian residuals and quality of variance will be tested. If the standard assumptions are not met, a transformation will be performed (i.e. logarithm transformation). Results will be brought back to the original units and reported as geometric means with their corresponding lower and upper confidence limits.

For the assessment of number of days on supplemental oxygen therapy (i.e. count data), a Poisson, Negative Binomial (NB), Zero-Inflated Poisson (ZIP), or Zero-Inflated Negative Binomial (ZINB) model will be used.

A result will be considered statistically significant at the $p < 0.05$ level of significance. All analyses will be performed using SAS version 9.4 (SAS Institute Inc., Cary, NC).

Sample Size Considerations:

The proposed sample size for this study is 228 subjects ($n=114$ per group). Based on data published by Gajdos, et al., the mean duration of hospitalization for bronchiolitis recorded in the study hospitals during previous years was 6.5 days and standard deviation = 3.5 days. For a type I error of 0.05 and a power of 0.80, for detecting a 20% decrease in duration of hospitalization, a total of 228 subjects would be included (114 subjects in each group).

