5.5 Duration of Study Participation

The duration of study participation will be from beginning of admission to the general inpatient pediatrics unit until the time of discharge from the general inpatient pediatrics unit. No follow up time period is required. This is a single phase pilot study.

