7.3.2 Enrollment/Baseline

Patients enrolled in the study will be based on history and physical examination and diagnosis. No additional procedures are required to assess or confirm whether the patients still meet the eligibility criteria.

Patients, based on history, physical examination, and diagnosis, who are receiving any additional treatments or have other underlying comorbidities affecting their respiratory system will be excluded from the study.

Enrollment/Baseline Visit (Visit 1, Day 0)

- Obtain informed consent of potential participant verified by signature on study informed consent form.
- Verify inclusion/exclusion criteria.
- Obtain demographic information, medical history and medication history.
- Record vital signs, results of examinations, other assessments.
- Administer the study treatment.
- Study participants will be provided information on the continued study treatment schedule as well as the process of evaluation and surveying on response to study treatments.

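### No common index time for eligibility: children weaned before enrolment are lost to the experimental arm, while similar children can count as controls

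*Combined protocol and SAP*

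**What the plan says.** **Experimental arm.** Section 5.1 opens with "In order to be eligible to participate in this study (experimental arm), an individual must meet all of the following criteria". The fourth criterion is that the child is on supplemental oxygen, with no time point. Under 5.4, "Informed consent will be obtained at time of admission within private space of patient room" and "Ample time will be provided for caregivers to decide on consent". Section 7.3.2 (Visit 1, Day 0) lists consent first, then "Verify inclusion/exclusion criteria", then the study treatment. Under 5.4 the care-team physicians are told within 1 hour after enrolment, and "investigators will obtain clearance from these providers to begin the study treatments". No limit is set on the clearance itself.

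**Control arm.** Section 5.1 continues: "Data collected for the control arm will be obtained via retrospective chart review for patients meeting the following inclusion criteria", with the same four criteria. Section 4.1 describes controls as patients from before the start date who, "beginning 12 months prior to start date of study, will be examined via retrospective chart review". Section 10.3 repeats this. There is no consent step and no index time.

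**Exclusions.** Section 5.2 gives both arms the same list, including intensive care, bronchodilators and antibiotics, without saying when in the stay it applies. Section 5.7.1 lets the investigator end participation when an exclusion newly develops or is newly recognised. Section 10.4.5 discounts participants who withdraw or are terminated early. Section 5.7.2 bars use of data from those who withdraw.

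**Clock and analysis.** Section 5.5 states: "The duration of study participation will be from beginning of admission to the general inpatient pediatrics unit". The endpoint definition in 4.2.1 gives no start time. Neither 10.4.2 nor 10.6 has a landmark, a delayed-entry adjustment or a matched index time.

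**The concern.** The same criterion works differently when applied at the bedside and when read from a finished chart. At the bedside, a child must still be on oxygen when the enrolment visit takes place. In a chart, nothing stops a reviewer from accepting a child who came off oxygen a few hours after reaching the unit. The two arms are then selected differently on a variable that is itself a primary endpoint and is tied to the other one.

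If outcomes run from unit arrival in both arms, every experimental child carries a stretch of oxygen and hospital time that had to be completed before entry. Controls carry no such guarantee. With historical controls, no randomisation and an unadjusted comparison, nothing later in the plan removes the difference.

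The exclusions have a related gap. A control chart shows the whole stay. An experimental child who newly meets an exclusion may, at the investigator's discretion, be terminated and then discounted. The plan does not ensure that the two processes remove the same kind of child.

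**Working it through.** **1. The plan's own figure.** Inputs from 10.5: mean stay 6.5 days, SD 3.5 days, 20% decrease, type I error 0.05 (two-sided assumed), power 0.80. The difference is 0.20 × 6.5 = 1.3 days.

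n per group = 2(1.960 + 0.842)² × 3.5² / 1.3² = 113.8, so 114. The stated 228 reproduces, and this point does not change it.

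**2. What the documents do not give.** They state neither the arrival-to-enrolment lag h nor the distribution of oxygen time. The only coefficient of variation (CV) available is for stay: 3.5 / 6.5 = 0.54. The Protocol Summary expects about 1 to 5 days of participation; I take 3 days, the middle, as an assumed mean oxygen time. A CV of 0.8 is a further assumption, to show more variable recovery.

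**3. Selection effect on oxygen time, with no treatment effect.** Let oxygen time X be gamma with shape k = 1/CV² and scale θ = mean/k. If only children with X > h enter the experimental arm, its mean is mean × S(h; k+1) / S(h; k). Here S(h; k) is the gamma upper-tail probability with shape k and scale θ. The share lost is 1 − S(h; k).

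| CV | k | θ (days) | Lag | S(h; k) | S(h; k+1) | Share lost | Rise in mean |
|---|---|---|---|---|---|---|---|
| 0.54 | 3.43 | 0.875 | 6 h | 0.9990 | 0.9999 | 0.1% | 0.1% |
| 0.54 | 3.43 | 0.875 | 12 h | 0.9910 | 0.9989 | 0.9% | 0.8% |
| 0.54 | 3.43 | 0.875 | 24 h | 0.9367 | 0.9845 | 6.3% | 5.1% |
| 0.8 | 1.5625 | 1.92 | 6 h | 0.9725 | 0.9986 | 2.7% | 2.7% |
| 0.8 | 1.5625 | 1.92 | 12 h | 0.9249 | 0.9926 | 7.5% | 7.3% |
| 0.8 | 1.5625 | 1.92 | 24 h | 0.8093 | 0.9635 | 19% | 19% |

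At CV 0.8, the 24 h rise is 3 × 0.19 = 0.57 day. For lags of 1 to 3 h at the same CV it is only 0.2% to 1.0%.

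**4. Effect on length of stay.** Stay was simulated as gamma or lognormal (2 million draws each), with oxygen time averaging 50%, 70% or 100% of stay. Only children whose oxygen time exceeded the lag were kept in the experimental arm. Ranges run over both distributions and all three shares.

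| Stay assumed | Target (20%) | 6 h | 12 h | 24 h |
|---|---|---|---|---|
| Mean 6.5, SD 3.5 days | 1.3 days | at most 0.01 day | 0 to 0.08 day | 0 to 0.38 day |
| Mean 3.0, SD 1.615 days (same CV) | 0.6 day | at most 0.04 day | 0 to 0.21 day | 0.06 to 0.72 day |

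Approximate power for a true 20% reduction is Φ((target − bias)/SE − 1.96), where SE = SD × √(2/114) and SD is the average of the two arms' SDs. With the 3.0-day mean, power stays at 0.80 or falls as low as 0.47 at 12 h, and lies between 0.72 and 0.01 at 24 h. With the planning values at 24 h it lies between 0.80 and 0.53.

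**5. Direction.** In every setting the selection lengthens the experimental arm or leaves it unchanged. It never shortens it.

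**The case against.** The strongest reply is that the plan intends a short lag. Patients are identified on admission, consent is planned at admission, and both the screening and the enrolment visits are labelled Day 0. If that is what happens, the figures above are negligible. This stands, and it limits the size of the point. It does not close it, because the time to decide is unbounded and nothing in the plan would show afterwards that the lag was short.

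Several stronger readings are tempting, and the documents do not support them:

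- **Provider clearance is an eligibility gate.** Section 5.4 places it after enrolment. A child weaned between enrolment and clearance is already enrolled. The plan does not say whether that child is analysed; clearance adds to the selection only if such children are dropped, which the broad wording of 10.4.5 would permit.
- **Controls qualify if on oxygen at any time in the chart.** The criterion reads the same in both arms. What can be said is that its timing is unspecified.
- **Fast recoverers enter only the control group.** With prompt consent, most would enter either arm.
- **Experimental exclusions count only up to enrolment.** Sections 5.7.1 and 10.4.5 allow later termination and discounting. The fault is that this is discretionary and has no matching rule for controls; its net direction cannot be read from the text.
- **The bias is very large.** A 50% rise in oxygen time needs a 2-day mean, a CV of 1.0 and a 24 h lag together. Nothing in the documents points to that combination.

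**Conclusion.** The point holds: eligibility has no common index time, and the plan as written can select the two arms differently on oxygen duration. The effect tends to lengthen the experimental arm's oxygen time and stay. It can mask a benefit or suggest harm. A reader might infer that it could also produce a spurious benefit; by itself it cannot. That statement assumes outcomes are counted from the same origin in both arms, which 4.2.1 does not say.

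The size rests on assumed lags and distributions. At a 3-day mean it is negligible for prompt consent (0.1% to 2.7% of mean oxygen time at 6 h) and becomes material near 12 to 24 h when stays are short or variable (0.8% to 7.3%, and 5% to 19%). The 20% benchmark is the plan's target for length of stay; it states none for oxygen time. This should be corrected before chart abstraction begins, with medium confidence that it matters in practice.

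**What to change.** 1. In 5.1, 5.2 and 10.3, record unit-arrival, enrolment and first-treatment times for each experimental child.
2. Assign each control an index time after unit arrival, drawn from the experimental arm's arrival-to-enrolment lags. Include the control only if still admitted and on oxygen at that time.
3. Apply every exclusion as of that time in both arms.
4. State in 4.2.1 one origin for both primary endpoints, the same in both arms.
5. Amend the analysis rules in 5.7.2 and 10.4.5 so that every enrolled child stays in the primary analysis as far as consent allows. This includes children weaned before first treatment, terminated under 5.7.1 or transferred later. Handle controls the same way. Without this step, controls who deteriorate after the index time would be kept while similar treated children could be dropped, which would favour the treatment.
6. Keep the unaligned comparison as a sensitivity analysis.

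**Cost.** Wording changes and a few timestamps. First-treatment time is in the medication administration record (6.1.10), and the time the oxygen order ends is already collected at the final visit (7.3.4). No additional enrolled children are needed. A few early-weaning controls are dropped, and the result then applies to children still on oxygen at the index time. The observed lags come only from children who were enrolled, so the screening log should also note those weaned before enrolment.

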The sub-investigators are pediatric medical residents with competent knowledge in the background and relevant literature of acute bronchiolitis and the standards of care. They have had experience in interaction with this patient population and have demonstrated competence in pediatric physician milestones. All physicians listed as sub-investigators have experience in clinical research and obtaining consent, maintaining confidentiality, as well as experience with safe data handling. Per the residency program and New York State requirements, pediatric residents are not required to obtain a state medical license during their training, thus the listed sub-investigators do not have a New York State medical license number.

This study currently does not have an identified biostatistician due to no biostatistician available at NYU Langone Hospital – Long Island. A data analysis plan has been developed. Once enrollment begins, data collection will occur, but this data will not be analyzed until a biostatistician has been identified and added to this study. A biostatistician will be added at the earliest time possible pending NYU Langone Hospital – Long Island and NYU Grossman Long Island School of Medicine's administration and the biostatistic department's process on filling this position.

2 Introduction, Background Information and Scientific Rationale

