7.3.3 Intermediate Visits

7.3.3.1 Intermediate visits

Intermediate visits will vary from participant to participant depending on their length of stay during their inpatient at admission.

Intermediate visits (once per shift during duration of admission)

- Record adverse events as reported by participant or observed by investigator.
- Record vital signs, to include respiratory rate, heart rate, and oxygen saturation.
- Record current supplemental oxygen support settings.
- Administer the study agent or provide additional medication to the participant, in accordance with schedule – nebulized 3% hypertonic saline treatments combined with 3 minutes of chest percussion therapy every 6 hours while on supplemental oxygen support.
- Record participant's adherence to treatment program.
- Record subjective responses from providers and caretakers on participants' clinical response to treatment.

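### Caregiver impressions are gathered face to face by the investigators and sub-investigators are not barred from rating, so the subjective ratings carry a high, unquantified risk of bias towards benefit

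*Combined protocol and SAP*

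**What the plan says.** **Caregivers.** Section 5.4 states: "Parents or caregivers or legal guardians of patients enrolled in this study will be approached at least once by the principal investigator or co-investigators", while the child is on study treatment. It adds that "this encounter is to serve as a means to conduct the subjective caregiver interview". The timing may vary, with a preference for at least 24 hours of treatment beforehand.

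**Physicians.** Also in 5.4, care-team physicians hear of the enrolment within 1 hour, and "investigators will obtain clearance from these providers to begin the study treatments". The section continues: "These physicians will also be notified at this time that they will be asked to answer subjective surveys".

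**Sub-investigators.** Section 1 (Key Roles) says: "The sub-investigators are pediatric medical residents with competent knowledge in the background and relevant literature of acute bronchiolitis".

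**Frequency.** Section 7.3.3.1, whose visits take place once per shift, includes the item "Record subjective responses from providers and caretakers". The schedule of events marks both surveys in its once-per-shift column. Sections 7.3.4 (day of discharge) and 7.3.5 (early termination) repeat the item.

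**Role in the analysis.** Section 4.2.2 makes caregiver and physician impressions secondary endpoints to be compared between control and experimental groups. Section 10.2 puts them in both the null and the alternative hypothesis.

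**Bias control.** Section 10.6 says that the study is unblinded and needs neither masking nor randomization. It does not mention the subjective ratings.

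**The concern.** A parent of a hospitalized infant is asked, in person, whether a treatment is helping, and the person asking runs the study of that treatment. The parent knows what the child is receiving, and the child is still receiving it. Courtesy and hope both push the answer towards a favourable one, and a poor impression is harder to voice to the investigator than on paper.

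The provider survey has a related weakness. If a listed sub-investigator is one of the residents caring for an enrolled child, the plan lets that person rate the response to a treatment they are themselves investigating.

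At stake is what the subjective results can be taken to mean. A high favourable rate would mix any effect of treatment with the way the question was put and by whom, and nothing in the plan would let a reader separate the two.

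**Working it through.** **1. Is there a figure to reproduce?** The only computed figure in the plan is the sample size in 10.5, and it concerns length of stay. The inputs are a mean of 6.5 days, an SD of 3.5 days, a 20% decrease (0.20 × 6.5 = 1.3 days), type I error 0.05 (two-sided reproduces the figure) and power 0.80. Per group, n = 2 × (1.96 + 0.8416)² × 3.5² / 1.3² = 2 × 7.849 × 12.25 / 1.69 = 113.8, rounded up to 114, or 228 in total. This matches the plan. It says nothing about the ratings, for which the plan gives no scale, spread, expected level or power. The check below therefore rests on reading the sections together.

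**2. Who asks, how and when (5.4).** The interviewer is the principal investigator or a co-investigator. The mode is an interview, and the moment is during study treatment. No independent interviewer or self-completed option is mentioned.

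**3. Who rates as a physician (1, 5.4).** Raters are physicians on the care team. Sub-investigators are pediatric residents, and the study has a single site and a single unit. No section bars a listed investigator from answering, and no section says that one will.

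**4. What protects the ratings (10.6 and elsewhere).** Section 10.6 is the place for such protection and has none for these endpoints. Oversight elsewhere is not independent: the principal investigator does the monitoring (9), audits adherence (10.4.5) and is the only member of the Steering Committee (14.1).

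**5. How often caregivers are asked.** Section 5.4 sets a minimum of one interview. Section 7.3.3.1 and the schedule have caregiver responses collected once per shift. A child staying several days could have one rating or many, and the plan does not say which rating would be analysed.

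**6. What the ratings are compared with.** Controls are patients from the 12 months before the start date, identified by retrospective chart review (4.1, 10.3). Section 4.2.2 itself says that the survey data cover enrolled patients only. The control group therefore has no ratings, and the between-group comparison in 4.2.2 and 10.2 cannot be made, however well the treated ratings are collected.

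**Result.** Steps 2 to 4 establish exposure to courtesy and expectation bias, most likely towards benefit, with no stated safeguard. Step 6 means that the level of the ratings in the treated group is the whole result, so the way they are collected bears directly on it.

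**The case against.** The strongest reply is that all this shows a risk and not a bias. The survey forms (Appendices 3 and 4) are not in the text reviewed, so their wording, scale and any anonymity cannot be judged. Only secondary endpoints are directly affected, and 5.5 describes the study as a pilot. In an open-label study every rater knows the treatment however the question is asked. All of this stands, and it limits the conclusion to a risk of unknown size. It does not remove the point, because 5.4 itself fixes the mode as an interview by the investigators, whatever the form looks like.

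A reader might infer more than the documents support in four ways:

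- **That sub-investigators do rate their own patients.** Section 5.4 speaks of investigators and care-team providers as separate groups, with the former seeking clearance from the latter and coordinating timing with them. Overlap is not excluded, but it is not documented.
- **That the bias has a particular size in percentage points.** Any such figure would need an assumed true favourable rate and an assumed courtesy rate, and the documents give neither.
- **That asking physicians for ratings distorts oxygen weaning or discharge.** Those physicians already know the treatment and must clear it. Section 7.1.2 leaves oxygen management to standard care, and no section links the survey to these decisions.
- **That the enrolment notice should go, or that provider ratings should move to after the discharge order.** The notice adds little to what the physicians already know. A rating made once the child is fit to go home has its own tilt towards benefit and loses the within-stay information. Section 7.3.4 already records responses on the day of discharge.

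**Conclusion.** The concern holds as a high risk of bias towards benefit in the caregiver and provider ratings, with no safeguard stated. For caregivers it follows directly from the mode of collection in 5.4. For providers it rests on a gap: the plan does not prevent a listed sub-investigator from being a rater. The direction is a judgement from the setting (in-person, unblinded, asked by the investigators), and the size cannot be derived from the documents. The conclusion assumes that the appendices contain no safeguard that overrides 5.4.

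Neutral collection would not rescue the planned comparison. Without control ratings, these data can only describe the treated group.

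**What to change.** - **Caregiver survey (5.4, 7.3.3, 7.3.4).** Make it a self-completed form, on paper or tablet, returned sealed, with no investigator present. The same form can serve the early termination visit in 7.3.5.
- **Provider survey (5.4).** State that no listed investigator or sub-investigator may complete one.
- **Frequency.** Reconcile the minimum of one caregiver contact in 5.4 with the once-per-shift collection in 7.3.3 and the schedule of events, and say which rating will be reported if there are several.
- **Analysis (4.2.2, 10.2).** Remove the subjective impressions from the between-group comparison and from the hypotheses. Report them descriptively for the treated group, and note that they are open-label and uncontrolled.

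**Cost.** A few lines of text and no extra staff. Self-completed forms may have a lower response rate than interviews, so the number returned should be reported with the results. Where a listed resident is on the care team, another physician on that team would have to answer.
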